4.4.4. Study Cohort

mPATH is designed to be given to all English or Spanish-speaking patients on clinic check-in. Therefore, our implementation outcomes cohort will include all adult (18 and over) English or Spanish-speaking patients who are seen in the study clinics in the 12 months following the initial clinic mPATH launch date. Our effectiveness outcome will include all English or Spanish speaking patients aged 50-74 who are eligible for CRC screening based on EHR records in the 12 months prior to and 12 months following the initial clinic mPATH launch date. We can capture all data needed for this cohort because all the clinics have searchable electronic health records.

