4.5 Pragmatic Trial

To determine mPATH-CRC’s effectiveness, we will nest a pragmatic trial within the implementation study. We will query the electronic health record (EHR) at each study clinic to identify unscreened individuals aged 50 – 74 who completed a clinic visit with a physician or advanced practice professional 4 to 12 months prior to the implementation launch date, and 0 to 8 months after the implementation kick-off launch date. Specific inclusion criteria are detailed in Section 3.0. We will then examine in the EHR whether these individuals complete CRC screening within 16 weeks of their index visit.

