6.0 Analytic Plan

6.1 Sample Size and Power

6.1.1 Primary outcome: Our primary objective is to assess differences in mPATH-CRC Reach proportion of participants who complete the mPATH-CRC program or have risk factors identified by mPATH-CheckIn) in the 6th month between the two implementation strategies. Using formulae found in Hemming et al.,⁷² **Table 3** shows the number of clinics necessary to detect differences in Reach ranging from .15 to .20 with 80% and 90% power for intraclass correlations (ICC) ranging from .03 to .08, assuming an average sample size per clinic of 30 with a cluster sample size coefficient of variation (CV) of 25%. These latter numbers are based on estimated numbers of eligible patients seen monthly, obtained from a

survey of the participating clinics. Since these data will be obtained from the EHR,

Table 3. Total number of clinics needed to detect the specified difference in Reach as a function of the power, ICC, and difference.

| Diff/ICC | 80% Power | | | | | | 90% Power | | | | | |
|----------|-----------|-----|-----|-----|-----|-----|-----------|-----|-----|-----|-----|-----|
| | .03 | .04 | .05 | .06 | .07 | .08 | .03 | .04 | .05 | .06 | .07 | .08 |
| .15 | 22 | 26 | 29 | 33 | 36 | 40 | 30 | 34 | 39 | 44 | 48 | 53 |
| .20 | 12 | 14 | 16 | 18 | 20 | 22 | 16 | 19 | 22 | 24 | 27 | 29 |

we will use all eligible patients at each site. We will recruit a total of 22 clinics, which will provide at least 80% power to detect a difference of 15% if the ICC is 0.03 or lower. If the ICC were as high as 0.08, we would have over 80% power to detect a difference of 20%. These calculations assume average utilization across all sites of 50%. Power increases as rates move away from 50% in either direction.

6.1.2 Effectiveness outcome: A secondary objective is to assess the effect of mPATH-CRC on screening rates (effectiveness) comparing 8 months of data prior to implementation to 8 months of data following implementation. The detectable difference (difference in screening rates pre vs post) depends on the sample size, power, ICC, and cluster sample size CV. We will assume a screening rate in the pre-implementation group of 15%, as observed in the control group in our R01 study.⁴⁵ Using SS/Power formulae for cluster designs^{72,73}, **Table 4** shows the differences in screening rates we will be able to detect

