with 80% and 90% power for ICCs ranging from 0.03 to 0.06, assuming an average monthly sample size of 30 patients per clinic in the EHR, a cluster sample size CV of 25%, and no change in the screening trends over time. Because of the diminishing return of cluster designs, additional patients have little effect on the detectable difference, although we will use all the patients in the EHR. We see that we will be able to detect a 10% difference in screening rates (15% vs 25%) with 80% power even if the ICC is as large as 0.04. We estimate that a minimum of 30 patients per clinic per month will meet inclusion criteria for this analysis (based on age, language, and screening status) and will be available through the EHR, so we will be amply powered for assessing the secondary aim.

To evaluate whether the effect of mPATH-CRC on screening rates differs by implementation strategy, the period (pre vs post) by strategy (“high touch” vs “low touch”) interaction can be evaluated. Based on the control group from the previous randomized-controlled efficacy study, we anticipate a screening rate of 15% for “low touch” and pre- implementation. An increase in

Table 4. Detectable difference in screening rates as a function of the Power and the ICC (22 Clinics)

| ICC | 80% Power | | | | 90% Power | | | |
|-----|-----------|------|------|------|-----------|------|------|------|
| | .03 | .04 | .05 | .06 | .03 | .04 | .05 | .06 |
| | .087 | .100 | .113 | .125 | .102 | .118 | .133 | .146 |

EFFECTIVENESS AND IMPLEMENTATION OF MPATH-CRC: A MOBILE HEALTH SYSTEM FOR

COLORECTAL CANCER SCREENING

Wake Forest Baptist Comprehensive Cancer Center (WFBCCC)

WFBCCC # TBD

the screening rate from 15% to 25% from pre to post, corresponds to an odds ratio (OR) of 3.

Similarly, assuming a screening rate in the “low touch” group of 15%, and a screening rate of 25% in the “high touch” group, also corresponds to an OR of 3. By design, we anticipate half of the patients being in the “high touch” group and half in the post period, and that strategy and period are independent. Based

on these assumptions, **Table 5** shows the interaction OR that can be detected with 80% power for ICCs ranging from 0.03 to 0.06, assuming an average monthly sample size of 30 patients per clinic in the EHR (for 8 months pre and 8 months post), a cluster sample size CV of 25%, and no change in the screening trends over time.

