Table 5. Detectable interaction odds ratio difference in screening rates as a function of the ICC (22 Clinics)

| ICC | 80% Power | | | |
|-----|-----------|-------|-------|-------|
| | .03 | .04 | .05 | .06 |
| | 2.903 | 3.462 | 4.097 | 4.819 |

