6.3 Analysis of Secondary Outcomes

The key secondary outcome of effectiveness of mPATH-CRC will be evaluated by comparing the proportion who complete CRC screening within 16 weeks of their index visit to the clinic between a pre-implementation cohort (months 12 - 4 before implementation) and a post-implementation cohort (months 1 - 8 after implementation). Similar to the model described for mPATH-CRC Reach above, effectiveness of mPATH-CRC will be evaluated using a mixed effects logistic regression model. For an overall assessment of the effectiveness, completing CRC screening within 16 weeks (Y/N) will be the patient-level outcome, implementation cohort will be the primary independent variable, site will be a random effect, and the stratification factor clinic size will be a covariate per the design. Pre- vs post-implementation changes will also be compared between the “high touch” and “low touch” implementation strategies and between dose levels defined based on mPATH™-CRC usage by incorporating interactions into the mixed effects logistic regression models. An interrupted time series analysis (segmented

EFFECTIVENESS AND IMPLEMENTATION OF MPATH-CRC: A MOBILE HEALTH SYSTEM FOR

COLORECTAL CANCER SCREENING

Wake Forest Baptist Comprehensive Cancer Center (WFBCCC)

WFBCCC # TBD

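### Rates of 15% and 25% give an odds ratio of 1.89, not 3, and Tables 4 and 5 match a layout with different clinics in each period, so both overstate what the effectiveness analysis needs to detect

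*Combined protocol and SAP*

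**What the plan says.** Section 6.1.2 assumes a pre-implementation screening rate of 15% and says that an increase in "the screening rate from 15% to 25% from pre to post, corresponds to an odds ratio (OR) of 3". It then takes 15% in low-touch and 25% in high-touch clinics, which it says "also corresponds to an OR of 3". Table 5, presented as resting on these assumptions, gives detectable interaction odds ratios of "2.903 | 3.462 | 4.097 | 4.819" for ICCs of 0.03, 0.04, 0.05 and 0.06 at 80% power, "assuming an average monthly sample size of 30 patients per clinic in the EHR (for 8 months pre and 8 months post", with a cluster-size CV of 25%.

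Table 4 gives detectable pre/post differences from 15%: .087, .100, .113 and .125 at 80% power, and .102, .118, .133 and .146 at 90%.

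On the design, section 6.1.2 describes "comparing 8 months of data prior to implementation to 8 months of data following implementation". Section 4.4.4 takes patients "in the 12 months prior to and 12 months following the initial clinic mPATH launch date", and section 4.5 queries each study clinic for visits "4 to 12 months prior to the implementation launch date, and 0 to 8 months after the implementation kick-off launch date". In section 6.3, "implementation cohort will be the primary independent variable, site will be a random effect".

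**The concern.** The odds ratio is an arithmetic slip, but it is stated twice and offered as an input to a table, so the question is whether the table is wrong too.

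The second question is layout. When each clinic contributes patients to both periods, the stable part of its screening level drops out of the pre/post contrast. It also drops out of the comparison of that contrast between arms. A calculation that charges the full between-clinic variance to these contrasts overstates the effect needed.

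Section 2.2.2 makes the pre/post comparison in high-touch against low-touch clinics the primary effectiveness analysis, and Table 5 is the plan's only statement of what that comparison can detect. Its smallest entry, 2.903, exceeds the whole effect of the efficacy trial cited in section 1.0: 30% against 15%, an odds ratio of (0.30/0.70)/(0.15/0.85) = 2.43. A reader would take the interaction to be practically untestable.

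**Working it through.** **Inputs from section 6.1.2.** Baseline 15%; 22 clinics, so 11 per strategy; 30 patients per clinic per month for 8 months, so 240 per clinic-period and 480 per clinic; CV 0.25, so 1 + CV² = 1.0625; ICC 0.03 to 0.06. Alpha is not stated for these tables; two-sided 0.05 is assumed.

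**1. Odds ratio.** (0.25/0.75)/(0.15/0.85) = 0.3333/0.1765 = 1.89. An odds ratio of 3 from 15% gives odds of 0.529, a rate of 34.6%.

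**2. Reproducing Table 4.** Design effect = 1 + (1.0625 × 480 − 1) × ICC; at ICC 0.04 this is 1 + 509 × 0.04 = 21.36. With 11 clinics of 480 against 11 other clinics of 480, the effective size per group is 5,280/21.36 = 247.2. The pooled-variance two-proportion formula then gives:

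| Layout | 80% power, ICC .03/.04/.05/.06 | 90% power |
|---|---|---|
| Printed | .087/.100/.113/.125 | .102/.118/.133/.146 |
| 11 vs 11 other clinics, 480 each | .0867/.1006/.1132/.1248 | .1016/.1181/.1329/.1466 |
| 22 clinics of 240 per period, unpaired | .0615/.0707/.0790/.0866 | .0719/.0827/.0925/.1015 |

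The 11-against-11 layout agrees within 0.001 in all eight cells. The 22-clinic layout does not, even with no pairing.

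**3. Reproducing Table 5.** This is a Wald test of the interaction in a 2×2 logistic model with four equal cells sharing an effective N of 10,560/design effect. At ICC 0.04 that is 494.4, or 123.6 per cell. With both main-effect odds ratios at 3, the cells are 15%, 34.6%, 34.6% and, at the solution, about 84.6%. The sum of 1/[p(1−p)] is 7.84 + 4.42 + 4.42 + 7.69 = 24.37. The standard error is √(24.37/123.6) = 0.444, and exp(2.80 × 0.444) = 3.47.

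| Main-effect odds ratios | ICC .03/.04/.05/.06 |
|---|---|
| Printed | 2.903/3.462/4.097/4.819 |
| Both 3 | 2.905/3.470/4.104/4.836 |
| Both 1.89 | 2.863/3.357/3.878/4.435 |

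The value 3 fits within 0.4%. The value 1.89 misses by 1.4, 3.0, 5.3 and 8.0%. So 3 was used.

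**4. Same 22 clinics in both periods.** Let c be the correlation of clinic effects between periods. The plan does not give it, so 0 to 1 is shown. Write B = 1.0625 × ICC, W = (1 − ICC)/240 and v = p(1 − p). The variance of a clinic's pre/post difference is (v₁ + v₂)(B + W) − 2cB√(v₁v₂). On the log-odds scale it is (1/v₁ + 1/v₂)(B + W) − 2cB/√(v₁v₂).

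*Overall difference* (22 clinics, noncentral t, 21 df, 80% power):

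| ICC | Printed | c = 0 | 0.5 | 0.8 | 1 |
|---|---|---|---|---|---|
| 0.03 | .087 | .065 | .048 | .034 | .021 |
| 0.04 | .100 | .074 | .054 | .037 | .021 |
| 0.05 | .113 | .083 | .060 | .040 | .021 |
| 0.06 | .125 | .091 | .065 | .043 | .021 |

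Power for 15% against 25% at c = 0 is about 96% at ICC 0.04 and 86% at ICC 0.06.

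*Interaction odds ratio* (11 clinics per arm, 20 df, 80% power; 15% before launch in both arms and 25% after launch in low-touch clinics, both assumed):

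| ICC | Printed | c = 0 | 0.5 | 0.8 | 0.9 | 1 |
|---|---|---|---|---|---|---|
| 0.03 | 2.903 | 2.32 | 1.89 | 1.61 | 1.49 | 1.37 |
| 0.04 | 3.462 | 2.61 | 2.05 | 1.68 | 1.54 | 1.38 |
| 0.05 | 4.097 | 2.89 | 2.20 | 1.76 | 1.59 | 1.39 |
| 0.06 | 4.819 | 3.18 | 2.35 | 1.83 | 1.63 | 1.40 |

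Power for an interaction odds ratio of 1.89 at c = 0/0.5/0.8/0.9/1 is about 56/80/96/99/>99% at ICC 0.03 and 34/55/84/95/>99% at ICC 0.06. A simulation of clinic-level logit differences (4,000 runs per setting) gave 58/81/97/99/>99% and 35/59/87/96/>99%.

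**The case against.** The plan nowhere says that different clinics supply the two periods. That layout is inferred from reproduction, with alpha assumed, and the reproductions are close rather than exact: .1006 would round to .101, not .100, and 4.836 is not 4.819. This stands as a caveat. Even so, twelve printed values agree this closely, and the natural same-clinic alternative misses Table 4 by a wide margin.

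The odds-ratio slip alone moves Table 5 by only 1.4 to 8.0%, and its direction depends on the cell rates. The row 2.86/3.36/3.88/4.44 keeps both of the plan's stated main effects, which places high-touch clinics at 25% before launch. With a period odds ratio of 1.89 and no strategy difference before launch, the table's own method gives 3.00/3.53/4.08/4.65: above the printed values at ICC 0.03 and 0.04, below them at 0.05 and 0.06. That is correct, so the slip by itself cannot be called conservative in every case. The layout error can.

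The same-clinic sizes also depend on method and unstated inputs. A normal-approximation version with both main effects at 1.89 gives 2.14/2.38/2.62/2.86 at c = 0 and about 1.29 at c = 1. A logit intercept that cancels fully gives 1.33. Holding low-touch clinics at 15% after launch lowers power for an odds ratio of 1.89 to 50/75/95% at ICC 0.03 and 30/50/82% at ICC 0.06 (c = 0/0.5/0.8). Appendix D reports that all practices stopped using mPATH in March 2020, so a correlation near 1 cannot be presumed. These points argue for showing a range. None brings the detectable interaction up to the printed row.

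Finally, ignoring pairing can be defended as cautious planning for a secondary outcome. That is fair, but the plan does not present the tables as upper bounds.

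**Conclusion.** The concern holds. The odds ratio is 1.89, the stated 3 is wrong in both places, and it fed Table 5. Tables 4 and 5 do not describe the planned same-clinic comparison. At every ICC shown and every c from 0 to 1, the detectable effects are smaller than printed; how much smaller depends on c.

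At c = 1, the case that a single site random effect as in section 6.3 implies, the detectable interaction odds ratio is about 1.4, less than half of any printed value. At c = 0 and ICC 0.06 it is still 3.18, so the interaction is not well powered under every assumption.

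The overall pre/post claim in section 6.1.2 stands and becomes stronger. The 22-clinic sample size rests on Reach in Table 3 and is not touched. The odds ratio needs no assumption. The same-clinic figures are a sensitivity range that rests on two-sided 0.05, the assumed cell rates and the assumed c. This should be fixed, but it does not threaten the trial.

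**What to change.** - Replace the odds ratio of 3 with 1.89 in both sentences of section 6.1.2.
- At minimum, refresh Table 5 with that input: 2.86/3.36/3.88/4.44 by the table's own method and the plan's two stated main effects. State the four cell rates used.
- Preferably, recompute Tables 4 and 5 for the same 22 clinics in both periods, about 240 patients per clinic-period. State alpha and the assumed between-period correlation of clinic rates, and show results over a range of it from 0 to 1.
- Say in the text that power for the period-by-strategy interaction depends on that correlation.

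The cost is two corrected figures in the text, two tables and a sentence. Sample size, analysis model and trial conduct stay as they are.

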6.2 Analysis of Primary Outcome

We will assess the primary hypothesis (that the “high touch” vs. “low touch” implementation strategy will result in greater use of the intervention) using a mixed effects logistic regression model with mPATH-CRC Reach (Y/N) as the individual-level outcome, implementation approach as the primary independent variable, site as a random effect, and the stratification factor clinics size as a covariate per the design. A descriptive approach will also be utilized where mPATH-CRC Reach is estimated and reported along with an exact 95% confidence interval for each month (for months 1-6 following implementation), and within socioeconomic strata for “high touch” and “low touch” clinics separately. In secondary analyses, we will assess effects of clinic-level covariates (e.g. volume, rurality, organizational culture) and patient level covariates (e.g. age, gender, race/ethnicity) on Reach. We will include arm-by-covariate interactions to determine if the effect of the implementation strategy differs depending on levels of the covariates. This secondary analysis will allow us to determine effects of the implementation strategy in clinics with varying organizational factors and populations. The proposed approach allows us to incorporate participant- and cluster-level covariates, but there are other analysis methods we could employ. For example, we could use a clinic-level analysis (e.g. analysis of covariance) on the mean implementation rates within each clinic, or another individual-level approach (e.g. generalized estimating equations). Alternative methods and their strengths and weaknesses are well-documented.⁷⁴⁻⁷⁶ These alternate approaches will be used in a sensitivity analysis to determine effects of the modeling assumptions on the results.

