1.0 Introduction and Background

In September 2016, the Cancer Moonshot Blue Ribbon Panel's report highlighted excessive mortality from colorectal cancer (CRC), the problems of health disparities, the need for interventions that inform patients of CRC screening tests, and the need for research to rapidly translate evidence-based CRC screening interventions into practice.¹ This study directly addresses all four of these Cancer Moonshot priorities by examining the implementation of an innovative mobile health (mHealth) CRC screening intervention that is accessible by members of health-disparate populations. Lessons learned from this study will inform the scale-up of this CRC screening intervention, as well as the implementation of other mHealth interventions.

Screening for CRC is widely recommended but underused. CRC screening tests are cost-effective, and they reduce both CRC mortality and incidence by detecting and removing pre-cancerous polyps.²⁻⁵ Regular screening for CRC beginning at age 50 is widely recommended by several groups, including the United States Preventive Services Task Force.⁶⁻⁹ Nonetheless, over 35% of Americans are unscreened.¹⁰

Screening rates are even lower among underserved populations, contributing to health disparities.^{10,11} Those with less education, limited income, or rural residences are less likely to be screened, and thus more likely to present with advanced-stage CRC and die from it.¹²⁻¹⁶ Limited health literacy, which affects over 33% of American adults further interfering with patients' ability to access, interpret, and apply health information to their care.¹⁷⁻²¹

Barriers to CRC screening include patient factors (lack of knowledge, low self-efficacy, fears, negative attitudes)²²⁻²⁸ and provider/system factors (lack of time, failure to offer screening options, lack of patient support).²⁹⁻³³ Meaningful increases in CRC screening will require an easily implemented intervention that addresses patient, provider, and system barriers while also being accessible to low income and low literacy individuals.^{34,35} We created our mPATH-CRC (mobile PAtient Technology for Health-Colorectal Cancer) intervention to tackle these needs.

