5.3 Secondary Outcomes

- 5.3.1 mPATH™-CRC Reach (by month): The proportion of patients aged 50-74 who are eligible for CRC screening who complete mPATH™-CRC or have risk factors identified by mPATH™-CheckIn in months 1-5 following implementation
- 5.3.2 mPATH™-CRC Reach (by socioeconomic strata): The proportion of patients aged 50-74 who are eligible for CRC screening who complete mPATH™-CRC or have risk factors identified by mPATH™-CheckIn in months 1-6 by socioeconomic strata; this outcome will also be calculated among CheckIn users only
- 5.3.3 mPATH™-CRC Adoption: The mean usage of mPATH™-CRC among staff and providers over the first 6 months following implementation; usage is calculated for each staff/provider as the proportion of times mPATH™-CRC is completed out of the total times mPATH™-CRC should have been launched.
- 5.3.4 mPATH™-CRC Acceptability, Appropriateness, and Feasibility: Mean Acceptability of Intervention Measure (AIM), Intervention Appropriateness Measure (IAM), and Feasibility of Intervention Measure (FIM) scores (68) for mPATH™-CRC as assessed on the 6-month clinic personnel survey
- 5.3.5 mPATH™-CRC Implementation Fidelity: The proportion of patients who use mPATH™-CRC and request a CRC screening test who have a test ordered or have the order dismissed (i.e., “self-order” feature is used as designed) in months 1-6
- 5.3.6 mPATH™-CRC Maintenance: The proportion of patients aged 50-74 who are eligible for CRC screening who complete mPATH™-CRC or have risk factors identified by mPATH™-CheckIn in months 7-12
- 5.3.7 mPATH™-CheckIn Reach: The proportion of patients aged 18 or older who complete mPATH™-CheckIn in months 1-6; this outcome will be calculated overall and within socioeconomic strata
- 5.3.8 mPATH™-CheckIn Adoption: The mean usage of mPATH™-CheckIn among staff and providers over the first 6 months following implementation; usage is calculated for front desk staff as the proportion of times mPATH™-CheckIn is completed out of the total times mPATH™-CheckIn should have been handed out; usage is calculated for nurses/providers as the proportion of times mPATH™-CheckIn is completed and data is transmitted to the EHR out of the total times mPATH™-CheckIn should have been handed out
- 5.3.9 mPATH™-CheckIn Acceptability, Appropriateness, and Feasibility: Mean AIM, IAM, and FIM scores for mPATH™-CheckIn as assessed on the 6-month clinic personnel survey

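### The exact 95% intervals planned for arm-level Reach ignore clinic; read as pooled binomial intervals, they cover about 85% (ICC .03) to 72% (ICC .08)

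*Combined protocol and SAP*

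**What the plan says.** Section 6.2 tests the primary hypothesis with a mixed effects logistic model that has "implementation approach as the primary independent variable, site as a random effect". It then adds a second layer: "A descriptive approach will also be utilized", in which "mPATH-CRC Reach is estimated and reported along with an exact 95% confidence interval for each month" from 1 to 6, and "within socioeconomic strata for “high touch” and “low touch” clinics separately". No clinic adjustment is mentioned for these intervals, and the exact method is not named.

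The same quantities are listed as secondary outcomes in section 5.3. Item 5.3.1 is Reach by month, "in months 1-5 following implementation". Item 5.3.2 is Reach "in months 1-6 by socioeconomic strata; this outcome will also be calculated among CheckIn users only".

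Section 6.1.1 sizes the trial on clustering of this outcome, "for intraclass correlations (ICC) ranging from .03 to .08, assuming an average sample size per clinic of 30" and a coefficient of variation (CV) of cluster size of 25%. Section 4.4.5 allocates 22 clinics in pairs, so 11 per arm. Section 1.0 gives the purpose: "Lessons learned from this study will inform the scale-up of this CRC screening intervention".

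**The concern.** For a single proportion, an exact interval ordinarily means Clopper-Pearson on the total count. That interval assumes independent patients, whereas section 6.1.1 assumes that patients in the same clinic are correlated. If clinics differ in how well they take up the program, 330 patients from 11 clinics carry much less information about Reach than 330 independent patients would.

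Section 6.2 specifies no other interval for the arm-level values of monthly and stratum-specific Reach. A health system planning roll-out would read these intervals to judge what uptake to expect, and would take Reach to be known more precisely than the plan's own assumptions allow.

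The point is limited to arm-level intervals. It makes no claim about the between-arm test, or about false differences between months or strata within an arm.

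**Working it through.** **Inputs.** All are from the plan unless marked as assumed.
- 22 clinics allocated 1:1, so 11 per arm (section 4.4.5)
- Mean 30 eligible patients per clinic per month, CV 0.25 (6.1.1), so 11 × 30 = 330 per arm per month
- ICC .03 to .08 and average Reach 50% (6.1.1)
- Two-sided alpha 0.05 for Table 3 (assumed, as it is not stated)
- Exact interval taken as Clopper-Pearson on the pooled count (assumed)

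**1. Reproduce Table 3.** The design effect is DE = 1 + ((1 + CV²)m − 1) × ICC = 1 + (1.0625 × 30 − 1) × ICC = 1 + 30.875 × ICC. This gives 1.926 at ICC .03, 2.544 at .05 and 3.470 at .08.

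Total clinics = 2 × [(1.96 + 0.842)² × (p₁q₁ + p₂q₂)/d²] × DE/30, with p₁ and p₂ placed symmetrically about 0.5.
- d = .15, ICC .03: 21.9 clinics, against 22 in the table
- d = .20, ICC .08: 21.8 clinics, against 22 in the table

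All 24 cells agree within one clinic, so this is the inflation on which the trial was sized.

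**2. Width.** The pooled Clopper-Pearson half-width at 165/330 is 5.5 points. Allowing for clinic, the half-width is c × √(0.25 × DE/330), with c = 1.96 (normal) or 2.228 (t, 10 df).

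**3. Coverage.** The normal approximation is 2Φ(1.96/√DE) − 1. The simulation used 11 clinics, gamma cluster sizes (mean 30, CV 0.25), beta-binomial outcomes at Reach 50% and 100,000 replicates per ICC.

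| ICC | DE | 330/DE | Half-width needed, normal | Half-width needed, t | Coverage, approximation | Coverage, simulated |
|---|---|---|---|---|---|---|
| .03 | 1.93 | 171 | 7.5 | 8.5 | 84.2% | 85.5% |
| .05 | 2.54 | 130 | 8.6 | 9.8 | 78.1% | 79.4% |
| .08 | 3.47 | 95 | 10.0 | 11.4 | 70.7% | 72.1% |

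With ICC 0 the same simulation gives 95.5%, so the loss comes from clustering.

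**4. Sensitivity.**
- Reach from 15% to 57.5%: coverage 85.3–85.8% at ICC .03 and 71.9–72.6% at .08
- Equal clinic sizes: 86.5% and 73.4%
- Normal clinic sizes (SD 7.5), 20,000 replicates: 85.1%, 79.4% and 71.9% at ICC .03, .05 and .08
- ICC .01 (assumed, below the plan's range): DE 1.31, coverage about 92%

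**5. Strata.** The plan gives neither their number nor their size. Assume 2 to 5 equal strata, all 11 clinics contributing, the same ICC range and Reach 50%.
- Reported monthly: coverage 90.6% to 82.8% with two strata and 94.3% to 91.6% with five (ICC .03 to .08)
- Pooled over months 1 to 6, as the wording of 5.3.2 suggests, with 180 patients per clinic split across strata: 69.5% to 50.2% with two strata and 84.0% to 68.1% with five

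**6. An alternative.** In the 20,000-replicate simulation, a t interval on the 11 clinic proportions covers 94.8–94.9% at ICC .03 to .08, with mean half-width 8.4 to 11.1 points.

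**The case against.** The strongest reply is that the plan itself calls these intervals descriptive. No test or decision uses them, and section 6.3 extends the clustered model to between-arm comparisons of the other binary outcomes. That is correct, and it limits the consequence. It does not supply a clustered interval for the arm-level values: section 6.3 and the sensitivity analyses in 6.2 concern comparisons and modelling assumptions. A 95% confidence level is a claim about coverage even in a descriptive table.

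Second, if the target is only the clinics observed, the shortfall disappears. Section 4.4.3 also says that clinics are chosen for diversity, so they are not a random sample of any population. This stands as a condition. The plan's random site effect and its scale-up aim nevertheless point beyond the observed clinics.

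Third, 0.08 is the top of a planning range, not an expected value. That is fair, but at the bottom of the range coverage is still about 85%.

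Fourth, the stratum figures rest on assumed inputs. The pooled ones also treat six months as separate sets of patients sharing one clinic effect. If clinic effects correlate only .6 to .8 between months (assumed), the lowest figure rises from 50% to about 54–58%. The direction is secure and the exact size is not.

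Fifth, the clinic-level t interval is not best everywhere. At Reach 30–50% it covers 94.4–95.1% for mean clinic sizes from 6 to 90. At Reach 10% with 6 patients per clinic it covers 90.5–92%, against 93–96% for the pooled exact interval, and 35–46% of the intervals run outside 0 to 1. It also weights clinics equally, whereas section 5.2 defines Reach over all eligible patients. These limits bear on the choice of method.

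**Conclusion.** The concern holds. As written, the monthly arm-level intervals would be labelled 95% but would cover about 85% at ICC .03, 79% at .05 and 72% at .08. They would show about ±5.5 points where ±7.5 to ±10.0, or ±8.5 to ±11.4 with t on 10 df, is warranted.

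This rests on two conditions: that exact means pooled Clopper-Pearson, and that the target is Reach in clinics like these. The monthly figures otherwise use the plan's own planning inputs. The stratum figures are indicative only. The primary mixed-model test, its power and the model-based arm comparisons are untouched. The intervals should be corrected before analysis, but the trial's main conclusion does not depend on them.

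**What to change.** In section 6.2, replace the exact interval with a 95% confidence interval that accounts for clustering by clinic, and name the method. Apply it to every monthly and stratum-specific arm-level Reach estimate. Suitable choices are:
- a t interval on clinic proportions (10 df per arm, fewer where fewer clinics contribute to a stratum), stating that clinics are weighted equally;
- generalized estimating equations (GEE) with a small-sample correction;
- marginal estimates from the mixed model.

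For small strata with low Reach, one of the last two is preferable to the clinic-level t interval. If a cluster-adjusted interval was always intended, the same sentence removes the ambiguity.

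The cost is one sentence, no new data and a little more analysis, because each month and stratum needs its own clinic-level summary or model. The intervals become wider.
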